## 8. SELECTION AND WITHDRAWAL OF PATIENTS

Patients with a genetic diagnosis consistent with SMA, bi-allelic deletion of SMN1 and 3 copies of SMN2 without the genetic modifier who demonstrate the ability to sit unassisted for 10 or more seconds but cannot stand or walk at the time of study entry will be enrolled in this clinical trial. Patients will be of any racial, ethnic, or gender background. Enrollment will be staggered with at least four weeks between patient injections for all patients in Cohort 1 and at least the first three patients in Cohort 2 and Cohort 3.

### 8.1. Patient Inclusion Criteria

Patients must meet all of the following inclusion criteria:

1. Patients  $\geq$ 6 months of age and  $\leq$ 60 months (1800 days) of age at time of dosing following diagnostic confirmation during screening period by genotype who demonstrate the ability to sit unassisted for 10 or more seconds but cannot stand or walk
  - Diagnostic confirmation by genotype includes lab documentation of homozygous absence of *SMN1* exon 7; with exactly three copies of *SMN2*
2. Negative gene testing for *SMN2* gene modifier mutation (c.859G>C)
3. Onset of clinical signs and symptoms consistent with SMA at  $<$  12 months of age
4. Able to sit independently and not standing or walking independently. Definition of sitting independently is defined by the World Health Organization- Multicentre Growth Reference Study (WHO-MGRS) criteria of being able to sit up unsupported with head erect for at least 10 seconds. Child should not use arms or hands to balance body or support position ([Wijnhoven 2004](#))
5. Meet age-appropriate institutional criteria for use of anesthesia and sedation, as determined necessary by the Investigator
6. Be up-to-date on childhood vaccines, including palivizumab prophylaxis (also known as Synagis) to prevent RSV infections, in accordance with the recommendations of the American Academy of Pediatrics ([AAP 2009](#))
7. Parent(s)/legal guardian(s) willing and able to complete the informed consent process

### 8.2. Patient Exclusion Criteria

Patients must not meet any of the following exclusion criteria:

1. Current or historical ability to stand or walk independently
2. Contraindications for spinal tap procedure or administration of IT therapy (e.g., spina bifida, meningitis, impairment, clotting abnormalities, or obstructive spinal hardware preventing effective access to CSF space) or presence of an implanted shunt for the drainage of CSF or an implanted CNS catheter
3. Severe contractures as determined by designated Physical Therapist(s) at screening that interfere with either the ability to attain/demonstrate functional measures (e.g., standing, walking) or interferes with ability to receive IT dosing
4. Severe scoliosis (defined as  $\geq$  50° curvature of spine) evident on X-ray examination

5. Previous, planned or expected scoliosis repair surgery/procedure within 1 year of dose administration
6. Use of invasive ventilatory support (tracheotomy with positive pressure) or pulse oximetry < 95% saturation at screening while the patient is awake, or for high altitudes > 1000 m, oxygen saturation < 92% while the patient is awake
  - Pulse oximetry saturation must not decrease  $\geq$  four percentage points between screening and highest value on day of dosing
7. Use or requirement of non-invasive ventilatory support for 12 or more hours daily in the two weeks prior to dosing
8. Medical necessity for a gastric feeding tube, where the majority of feedings are given by non-oral methods (i.e., nasogastric tube or nasojejunal tube) or patients whose weight-for-age falls below the 3rd percentile based on World Health Organization (WHO) Child Growth Standards ([Onis 2006](#)). Placement of a permanent gastrostomy prior to screening is not an exclusion.
9. Active viral infection (includes human immunodeficiency virus [HIV] or serology positive for hepatitis B or C, or Zika virus)
10. Serious non-respiratory tract illness requiring systemic treatment and/or hospitalization within two weeks prior to study entry
11. Respiratory infection requiring medical attention, medical intervention or increase in supportive care of any manner within four weeks prior to study entry
12. Severe non-pulmonary/respiratory tract infection (e.g., pyelonephritis or meningitis) within four weeks before study dosing or concomitant illness that in the opinion of the Principal Investigator creates unnecessary risks for gene transfer such as:
  - Major renal or hepatic impairment
  - Known seizure disorder
  - Diabetes mellitus
  - Idiopathic hypocalciuria
  - Symptomatic cardiomyopathy
13. History of bacterial meningitis or brain or spinal cord disease, including tumors, or abnormalities by magnetic resonance imaging (MRI) or computed tomography (CT) that would interfere with the lumbar puncture (LP) procedures or CSF circulation
14. Known allergy or hypersensitivity to prednisolone or other glucocorticosteroids or their excipients
15. Known allergy or hypersensitivity to iodine or iodine-containing products
16. Concomitant use of any of the following: drugs for treatment of myopathy or neuropathy, agents used to treat diabetes mellitus, or ongoing immunosuppressive therapy, plasmapheresis, immunomodulators such as adalimumab, or immunosuppressive therapy within 3 months of study dosing (e.g., corticosteroids, cyclosporine, tacrolimus, methotrexate, cyclophosphamide, IV immunoglobulin, rituximab)

17. Inability to withhold use of laxatives or diuretics in the 24 hours prior to dose administration
18. Anti-AAV9 antibody titers >1:50 as determined by enzyme-linked immunosorbent assay (ELISA) binding immunoassay
  - Should a potential patient demonstrate anti AAV9 antibody titer > 1:50, he or she may receive retesting within 30 days of the screening period and will be eligible to participate if the anti AAV9 antibody titer upon retesting is ≤ 1:50
19. Clinically significant abnormal laboratory values (gamma glutamyl transferase [GGT], ALT, and AST, or total bilirubin > 2 × ULN, creatinine ≥ 1.0 mg/dL, hemoglobin [Hgb] < 8 or > 18 g/dL; white blood cell [WBC] > 20,000 per cmm) prior to gene replacement therapy. Patients with an elevated bilirubin level that is unequivocally the result of neonatal jaundice shall not be excluded.
20. Participation in recent SMA treatment clinical trial or receipt of an investigational or approved compound product or therapy received with the intent to treat SMA (e.g., valproic acid, nusinersen) at any time prior to screening for this study
  - Oral beta agonists must be discontinued 30 days prior to dosing
  - Inhaled albuterol specifically prescribed for the purposes of respiratory (bronchodilator) management is acceptable and not a contraindication at any time prior to screening for this study
21. Expectation of major surgical procedures during the 1-year study assessment period (e.g., spinal surgery or tracheostomy)
22. Inability or unwillingness to comply with study procedures or inability to travel for repeat visits
23. Unwillingness to keep study results/observations confidential or to refrain from posting confidential study results/observations on social media sites
24. Refusal to sign consent form

### **8.3. Patient Withdrawal Criteria and Discontinuation**

Patients meeting the following criteria will be withdrawn:

- Death
  - Autopsies will be requested of any patients, with the exception of untreated patients, that expire following participation in a gene transfer study
- Failure to comply with protocol-required visits or study procedures for 3 or more consecutive visits that are not rescheduled, unless due to hospitalization
- Parent(s)/legal guardian(s) withdraws consent
- Investigator discretion

Early termination procedures should be completed within 14 days for any patient who prematurely discontinues the study for any reason. Patients who terminate the study early for reasons other than death will be offered enrollment in a long-term follow-up study.

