## **9.3. Treatment Compliance**

AVXS-101 will be administered as a one-time IT injection.

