Based on an ongoing assessment of safety and efficacy data from patients treated with the  $1.2 \times 10^{14}$  vg dose, an option for testing of a third dose (Dose C) will be considered. A meeting of the DSMB will be called to obtain agreement on the safety of escalating to a higher dose prior to proceeding. If, based on all available data, this is judged to be necessary, three (3) patients  $<$  60 months of age will receive  $2.4 \times 10^{14}$  vg of AVXS-101 (Dose C). If agreement is obtained from the DSMB, there will again be a four-week interval between dosing of the first three patients receiving Dose C, as in Cohorts 1 and 2. Safety data will be reviewed by the DSMB during quarterly meetings; following enrollment of the first three (3) Dose C patients and based upon available safety data, a decision will be made whether to: a) stop due to toxicity, or b) continue to enroll an additional 21 patients until there are a total of twelve (12) patients  $>$  6 months and  $<$  24 months and twelve (12) patients  $\geq$  24 and  $<$  60 months that have received Dose C.

All patients enrolled in Cohort 1 (Dose A) and Cohort 2 (Dose B) will be followed for a total of 12 months. Patients enrolled in Cohort 3 (Dose C) will be followed for a total of 15 months. The primary analyses for efficacy will be assessed when all patients in each age group reach 12 months post-dose and the primary analyses for safety will be assessed when the last patient of

Cohort 3 reaches 15 months post-dose (and database lock will be performed at the time point at which the last patient reaches 15 months post-dose). An additional analysis of efficacy and safety data was conducted when the last Cohort 2 patient completed the 12 month visit.

Safety will be assessed through monitoring AE reports and concomitant medication usage, and by conducting physical examinations, vital sign assessments, cardiovascular evaluations, laboratory evaluations, and pulmonary examinations. Patients will be observed at the hospital for 48 hours post intrathecal injection. Patients will return for follow up visits on Days 7, 14, 21, and 30. Patients will return monthly thereafter, following the Day 30 visit, according to the Schedule of Assessments. Patients in Cohort 3 who were enrolled into the study after Protocol Version 8 (Amendment 7) went into effect will return for follow up visits on Days 44 and 72 for laboratory assessments (liver function tests only).

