## 5.5. Per Protocol or Evaluable Set

### 5.5.1. Efficacy Completer Analysis Set

The Efficacy Completer Analysis Set (ECAS) consists of all treated patients who complete 12 months following AVXS-101 dose procedure. The end of study visit can be conducted either remotely or at the study site.

Patients who terminate the study early will not be included in ECAS.

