### **6.3. Missing Data**

Patients are allowed to withdraw from the study at any time. Analysis of quantitative and categorical variables will include data from patients with non-missing values. For continuous variables, a MMRM model may be used for the comparison between AVXS treated patients and the matching PNCR cohort.

Imputation of missing or incomplete dates will only be performed on AEs and concomitant medications for determining the timing relative to the dose of study product unless otherwise specified. The rules of imputation of missing dates are specified in Table 1 and Table 2. Partial or missing dates will be listed as recorded in the electronic case report form (eCRF). All imputed dates will be no earlier than the patients' birth date.

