time variable. Age at baseline will be used as a covariate. The probability of the ability to stand alone over time will be estimated using Kaplan-Meier methods. A Cox regression model will be used to obtain the hazard ratio with 95% CI for AVXS-101 Dose B to the data from PNCR. In this analysis, patients will be censored at the date of their End of Study visit.

All of the efficacy analyses stated above may be repeated using the ECAS as a sensitivity analysis, in the event the ECAS contains a subset of patients of the ITT Set.

If necessary, an additional set of sensitivity analyses may be conducted to include patients who demonstrated the developmental milestone of standing alone (Bayley-III, Gross Motor Subtest #40) which occurred after but within 3 months of the upper bound of the Month 12 visit window (day 374) due to COVID-19 disruptions.

In the first sensitivity analysis, the proportion of patients  $\geq$  6 months and  $<$  24 months of age at time of dosing that achieve the developmental milestone at any post-baseline visit (considering the expanded 3-month window) will be summarized overall and by dose. The corresponding p-value from a Fisher's exact test will be computed for the comparison between AVXS-101 Dose B and PNCR data. The summary and statistical analysis will be conducted using the ITT Set. The difference in the proportions between AVXS-101 and PNCR will be summarized and the exact 95% CIs will be provided accordingly.

In the second sensitivity analysis, the time from dosing to achieving the ability to stand alone will be summarized for patients overall and by dose in the ITT Set. The study day will be used as the time variable. Age at baseline will be used as a covariate. The probability of the ability to stand alone over time will be estimated using Kaplan-Meier methods. A Cox regression model will be used to obtain the hazard ratio with 95% CI for AVXS-101 Dose B and PNCR. In this analysis, patients who demonstrated the developmental milestone within the expanded 3-month window after Month 12 will be censored at the last attended visit prior to when the Month 12 visit was scheduled to occur.

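### Protocol 8.3 makes withdrawal mandatory for a child already dosed once three consecutive visits are missed without rescheduling or hospitalization, so the Month 12 outcome and remaining safety tests go uncollected although no study product is left to stop

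*Protocol*

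**What the plan says.** Protocol section 8.3 opens its list with "Patients meeting the following criteria will be withdrawn", so the wording is mandatory. One criterion is "Failure to comply with protocol-required visits or study procedures for 3 or more consecutive visits that are not rescheduled, unless due to hospitalization". Death, withdrawal of consent and investigator discretion are separate bullets.

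The treatment is a single administration. Protocol section 9.3 states: "AVXS-101 will be administered as a one-time IT injection".

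SAP section 3.5 gives the first outpatient visits: "Patients will return for follow up visits on Days 7, 14, 21, and 30". Protocol Table 3 has the same days, with a window of ±2 days on the early visits.

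After withdrawal, section 8.3 provides: "Early termination procedures should be completed within 14 days for any patient who prematurely discontinues the study for any reason". It also offers enrolment in a long-term study, which section 7.1 places under a separate protocol. Protocol section 13.4 asks for related serious adverse events that the investigator discovers after the study. No Month 12 assessment is planned for a withdrawn child.

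In the SAP, the ITT Set (5.4.1) and the Safety Analysis Set (5.3) keep every dosed child. Section 6.3 says: "Analysis of quantitative and categorical variables will include data from patients with non-missing values". Section 6.4.3 scores a child who has not shown standing by 12 months as a non-responder. Section 5.5.1 says: "Patients who terminate the study early will not be included in ECAS".

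**The concern.** In a trial with repeated dosing, a rule of this kind can serve to stop treatment in a patient who cannot be monitored. Here the only dose has already been given and cannot be undone. Applied to a dosed child, the rule ends observation and nothing else.

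Because it counts visits, the rule is strictest when visits are closest together, in the first weeks after dosing. At Day 21 the child is still in the prednisolone period (Protocol 9.2.1), before the Day 30 and later laboratory tests, and within the month of platelet monitoring on which Protocol 5.5 relies. Section 12.1 names safety as the primary outcome.

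Three things are at stake:

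- **Older group:** the Month 12 HFMSE, the primary endpoint, is not collected.
- **Younger group:** a child who would have stood or walked later in the year counts as a failure.
- **Both groups:** the remaining scheduled in-trial safety tests are not done, even if the family is willing to come back.

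**Working it through.** **1. How quickly the rule can be met.** Inputs: visit days and windows (Protocol Table 3), nominal days for Months 12 and 15 (SAP Tables 4.1 and 4.2).

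- Nominal span of the first three outpatient visits: 21 − 7 = 14 days.
- With ±2-day windows: shortest (21 − 2) − (7 + 2) = 10 days; longest (21 + 2) − (7 − 2) = 18 days.
- Follow-up forgone after Day 21: 360 − 21 = 339 days to Month 12. For Cohort 3, 450 − 21 = 429 days to Month 15.
- For comparison, three monthly visits (Days 30, 60, 90) span 90 − 30 = 60 days.

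**2. What the early termination visit can replace.** Procedures within 14 days of Day 21 fall by about Day 35. SAP Table 4.1 maps Days 1 to 44 to Month 1, and Table 4.2 maps Days 1 to 38 to Month 1. That visit cannot supply a Month 12 value. The first scheduled post-baseline HFMSE is at Day 30, so a child withdrawn at Day 21 brings at most one post-baseline score to the repeated-measures model.

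**3. Weight of one child.** 12 Dose B children are planned per age group: 1/12 = 8.3%.

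**4. The plan's power, reproduced.** Inputs: two-sided 5% level; standing 85% v 14% and walking 60% v 10% in the younger group (Protocol 14.4); HFMSE change +8 v −1.33, SD 4.32 (Protocol 14.4), or v −1.13, SD 4.90 (SAP 3.7); 51 and 15 natural history controls (SAP 5.6.1).

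For the proportions, with L of the 12 treated children lost before the milestone and scored as non-responders:

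power = Σₐ Σᵦ Bin(a; 12 − L, p₁) · Bin(b; 51, p₀), summed over pairs where Fisher's exact p for a/12 v b/51 is ≤ 0.05 and a/12 > b/51.

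For HFMSE: noncentral t with 12 − L + 15 − 2 degrees of freedom and noncentrality δ / (SD·√(1/(12 − L) + 1/15)). With L = 0, √(1/12 + 1/15) = 0.387:

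- SD 4.32: 9.33 / (4.32 × 0.387) ≈ 5.58, power 99.97%.
- SD 4.90: 9.13 / (4.90 × 0.387) ≈ 4.81, power 99.6%.

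Standing gives 99.9% and walking 94.3%. The plan's claim of more than 90% is confirmed in every case.

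**5. Power with children lost.** The documents give no dropout rate, so L = 1 to 4 is an assumed range.

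| Lost of 12 | Expected standing rate, 85% × (12 − L)/12 | Standing power | Walking power | HFMSE power, SD 4.32 | HFMSE power, SD 4.90 |
|---|---|---|---|---|---|
| 0 | 85.0% | 99.9% | 94.3% | 99.97% | 99.6% |
| 1 | 77.9% | 99.6% | 90.6% | 99.9% | 99.4% |
| 2 | 70.8% | 98.7% | 85.1% | 99.9% | 99.2% |
| 3 | 63.8% | 96.3% | 77.0% | 99.8% | 98.8% |
| 4 | 56.7% | 90.2% | 66.0% | 99.7% | 98.2% |

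The HFMSE columns treat a lost child as contributing nothing. They therefore ignore any earlier scores that the repeated-measures model would use.

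**The case against.** The strongest reply is that the rule is milder than it looks. A visit that is rescheduled, for whatever reason, drops out of the count, and so does one missed because of hospitalization. Exclusion criterion 22 already screens out families unable or unwilling to comply or travel. Collected data are kept, and scoring a withdrawn child as a non-responder works against the drug. Early termination procedures, the long-term study and later reporting of related events recover part of the safety information. All of this stands, and it makes the point smaller. It does not replace the Month 12 endpoint or the scheduled tests. Section 8.3 also does not say how late a rescheduled visit may be, so it is unclear how much relief rescheduling gives when visits are a week apart.

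A reader might infer more than the documents support:

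- **That any three missed visits force withdrawal, with hospitalization the only excuse.** The rescheduling exception is in the criterion itself.
- **That the child's data are thrown away.** The child stays in the ITT and safety sets. The repeated-measures model in SAP 8.1.2 uses earlier HFMSE values, and SAP 8.4.2 averages all available scores. Exclusion from the completers set affects only sensitivity analyses that may be run.
- **That Days 44, 60 and 72 are another short run threatening the 12 Dose B HFMSE values.** SAP 3.5 limits Days 44 and 72 to Cohort 3 patients enrolled after Amendment 7. SAP 2.2.1 reports four Cohort 3 children, all in the younger group and summarized descriptively.
- **That the COVID-19 provisions contradict the rule.** SAP 5.5.1 allows a remote end-of-study visit, and SAP 8.1.1 may count milestones seen late but "within 3 months of the upper bound of the Month 12 visit window (day 374) due to COVID-19 disruptions". Neither says whether children with three unrescheduled missed visits were kept.

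**Conclusion.** The point holds in a limited form and is a cheap improvement. As written, section 8.3 requires a dosed child to leave the study for missed visits, possibly within 14 days of the first outpatient visit, with nothing gained from stopping product. The price is a Month 12 HFMSE that is never measured, a response rate biased downward for standing and walking, and scheduled in-trial safety tests not done.

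Each Dose B withdrawal concerns 8.3% of its age group. The primary endpoints are not at risk on power: with up to 4 of 12 lost, standing keeps 90.2% and HFMSE at least 98%. The secondary walking endpoint in the younger group is more exposed, at 85.1% with two lost and 66.0% with four.

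These figures rest on the plan's own effect sizes, on an assumed 1 to 4 losses, and on losses that occur before the milestone and are unrelated to the outcome the child would have had. The documents do not say how many children were withdrawn under this rule, and the Day 7, 14 and 21 sequence is a worst case, not an observed one. Cohort 3 enrolment has already ended early (SAP 2.2.1), which limits what a change can recover in this trial.

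**What to change.** In Protocol 8.3:

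- Remove missed visits or procedures as a mandatory reason for withdrawing a dosed patient, and record them as protocol deviations.
- State that a dosed child stays in follow-up until consent is withdrawn, death, investigator decision (the existing bullet), or documented loss to follow-up after repeated failed attempts at contact.
- State that, whatever was missed, the site still attempts the remaining scheduled safety tests, the Month 12 HFMSE and milestone assessment, and the end-of-study visit.

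Do not keep a version of the rule for children not yet dosed. Table 3 has only Screening and Day −1 before dosing on Day 1, so three visits cannot be missed by then.

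The cost is a few sentences of protocol text, some extra site effort to re-contact families, and some irregularly timed visits in the data. No dose, visit schedule or treatment rule changes.

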## 9. TREATMENT OF PATIENTS

### 9.1. Description of Study Product

The biological product is a non-replicating recombinant self-complementary adeno-associated virus serotype 9 (AAV9) containing the cDNA of the human SMN gene under the control of the cytomegalovirus enhancer/chicken- $\beta$ -actin-hybrid promoter (CB). The AAV ITR has been modified to promote intramolecular annealing of the transgene, thus forming a double-stranded transgene ready for transcription. This modified ITR, termed a “self-complementary” (sc) ITR, has been shown to significantly increase the speed of which the transgene is transcribed, and the resulting protein is produced. Cells transduced with AVXS-101 (formerly scAAV9.CB.hSMN) express the human SMN protein.

